## **I-Administrative Information**

**1-Title: Assessment of the anterior loop of inferior alveolar nerve in a sample of Egyptian Population using CBCT: An Observational Cross-Sectional Study.**

**2-Protocol Registration:**

Registered at [www.clinicaltrials.gov](http://www.clinicaltrials.gov)

**ID:** .....

**3-Protocol Version:** 2nd version

**4-Funding:** self-funding

**Roles of the investigator:**

- Preparing the technical proposal
- Assuring that the design is appropriate to the proposed question.
- Identifying the need for sub-recipient agreements.
- Ensuring that the used procedures are consistent with sound research design and do not unnecessarily expose subjects to risk/harm.
- Being responsible for all required actions to manage and complete the scientific and programmatic aspects of the project (including data collection and assessment).
- Ensuring the integrity and safeguarding of notebooks and scientific data. Ensuring the completion, accuracy and timeliness of programmatic (technical) reports.

**Roles of Chief Supervisor:**

- Assisting the candidate -in association with the co-supervisor -to prepare a full research plan that can be completed and written up within the prescribed period of study, and to seek approval for that proposal.
- Establishing a research plan with the investigator, in which the work is completed.
- Discussing the work done through meetings or exchanging email messages if the candidate is in a remote location, at least once per month. Assisting the candidate by regularly checking the records of data and observations and suggesting improvements where appropriate.

- Providing constructive criticism and advice on submitted written drafts within agreed time frames.
- Supporting the candidate in the preparation for thesis defense.
- Facilitating timely completion of the candidate's study and ultimate completion of the thesis.

**Roles of Assistant Supervisor:**

- Monitoring the progress of the student's research through regular formal supervisory meetings and ensuring that the research student keeps an agreed record of these meetings.
- Being accessible at mutually convenient times when the research student may need advice.
- Performing the blind assessment during the data collection stage.
- Giving detailed advice on the necessary completion dates of successive stages of the work so that the thesis can be submitted within the relevant maximum registration period.
- Reading and commenting on the whole of the final draft of the thesis, provided that this is presented within a reasonable and agreed time frame, and ensuring that the research student is aware that the thesis must comply with all relevant regulations, including those on word length, format, and binding.

**II-Introduction**

**6. a. Scientific Background:** The proper knowledge of anatomical structures and their precise position is of a paramount importance for different dental specialties. The inferior alveolar nerve (IAN) canal is one of the most important anatomical landmarks in the mandible *Shaban et al., 2017*. By definition the inferior alveolar nerve (IAN) is a terminal division of the mandibular branch of the trigeminal nerve, it is confined within the mandibular canal and innervates all the mandibular teeth. The IAN initiates from the mandibular foramen and goes obliquely downward and forward in the ramus, and then horizontally within the body of the mandible. The IAN gives off the mental nerve, which exits the mandible through the mental foramen, supplying sensory branches to the chin, lower lip, mucous membranes and the gingiva; from the midline to about the second premolar region. It then continues its path anteriorly and turn into the mandibular incisive nerve, which innervates the mandibular canines and incisors *Siddiqui et al. 2018*. Before leaving the mental foramen and branching into the incisive nerve, the IAN may continue anteriorly and form an anterior loop (Al). This anterior loop is the part where the IAN directs mesially and occlusally before reversing direction and coursing distally towards the mental foramen *Ragu et al., 2019*. During implant planning and other surgical procedures knowing the presence of the anterior loop and its length is very crucial to avoid its injury. Specially concerning implantology where the location of the mental foramen and anterior loop determines the most distal point for implant placement in the

interforaminal area; in order to avoid any injury resulting in sensory disturbances in this area

**Panjnoush et al., 2016**

Recently, several studies have been published discussing the prevalence and length measurement of the anterior loop in many populations. However, no published researches were done on the Egyptian population. Therefore, this study is designed to assess the presence of the anterior loop and its length in a sample of Egyptian population using CBCT.

### **PO question**

**P:** mandible quadrants in Adult Egyptian Population.

**O:** Presence of the anterior loop of the inferior alveolar nerve; and its length in the mandibles of adult Egyptian population

	Outcome Measured	Measuring Device	Measuring Unit
Primary Outcome	Prevalence of the anterior loop	CBCT axial cuts (Ondemand 3D software)	Categorical nominal data Percentage (%)
Secondary Outcomes	length of the anterior loop	Built in measuring tools (axial cuts) in Ondemand 3D software “MPR* module”	mm
	Mesial extension of the anterior loop	Cross-sectional cuts on Ondemand 3D software “DVR** module”	mm

\* MPR: Multiplanar Reformatting

\*\* DVR: Direct Volume Rendering

### **Research question:**

How frequent is the anterior loop and how long its mesial extension is in a sample of Egyptian population?

## 6b. Review of literature

[figure not shown]
List of main databases used in search:

- ✓ Pubmed
- ✓ Google Scholar

Keywords:

[figure not shown]
Anterior Loop, Mandibular Canal, Mental Foramen, CBCT, Maxillofacial Anatomy, Dental Implants.

In **1994 Solar et al** classified the mental nerve path of the IAN canal into three types; where type I is defined as a Y-shaped anatomy of the incisive branch & the mental branch with absence of the anterior loop, while type II is a T-shaped anatomy with the incisive branch being perpendicular to the mental branch still with the anterior loop's absence, and finally type III is defined as a Y-shaped anatomy with the presence of the anterior loop (Figure 1).

**Figure 1: IAN Types (Demir et al 2015)**

According to **Bavitz et al. 1993 & Misch 1999** the IAN's anterior loop is defined as the structure where the mental neurovascular bundle passes inferior and anterior to the mental foramen then loops backwards to exit the mental foramen (Figure 2).

**Figure 2:** Schematic diagram showing key image of anterior loop of IAN (*Siddiqui, et al 2018*)

Different methods were used to assess the anterior loop including cadavers, dry skulls, panoramic radiographs, medical CT and CBCT; which is the reason behind the considerable variation of the prevalence and average length of the anterior loop mentioned in the literature where the mean length ranges between 0.1 mm & 6.92 mm **Patterson 2015**. In addition to the effect of different races, age and gender. **Ngeow et al 2009** stated that several authors have suggested the limitation of panoramic radiograph regarding the visualization of the anterior loop for the purpose of implant planning due to the high percentage of false-positive and negative findings compared to cadaveric dissection data owing to its limitation as a two dimensional radiographic method. Bringing us to the fact that three dimensional imaging techniques such as medical CT, Magnetic Resonance Imaging (MRI) and Cone beam CT evade this draw back **Ngeow et al 2009 & Nair et al 2013**.

**Nair et al 2013** stated that CBCT surpasses medical CT in its significantly lower dose with producing high resolution, superimposition and magnification free undistorted 3D images of the maxillofacial anatomy.

Therefore it is the method of choice for assessment of the anterior loop before surgical intervention as mentioned by **Demir et al 2015, Moghdam et al 2017 & Siddiqui et al. 2018**.

### **6c. Statement of the Problem**

A high percentage of iatrogenic damage to the mental nerve occurs due to the unawareness of dental clinicians with the presence of an IAN's anterior loop in the interforaminal area during implant placement or other surgical procedures such as tumor or tooth impaction removal; leading to its injury. Therefore, dental clinicians should know the prevalence of the anterior loop in different populations in addition to having a proper case examination and planning using CBCT.

## **Specific Objectives:**

To detect the prevalence of anterior loop and measure its length in relation to gender effect in a sample of the Egyptian population.

## **Hypothesis: null**

## **III -Methods**

### **A) Study design and setting**

**7- Study Design:** An observational Cross-sectional Study

### **8- Setting and Location:**

The CBCT data of this study will be obtained from the CBCT data base available at a private radiographic centre “ORASCAN Oral & Maxillofacial Imaging Centre” located in Cairo, Egypt. Being a retrospective study, CBCT images of Egyptian patients who have already been subjected to CBCT examination as part of their dental diagnosis and/or treatment planning during the years 2018-till present will be included according to the proposed eligibility criteria.

### **B) Participants:**

Based on sample size calculation, a sample of 192 CBCT images of mandible quadrants belonging to Egyptian individuals will be examined. The selection of the scans to be included will be based on the following eligibility criteria.

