### **9- Eligibility criteria and selection method:**

#### **✓ Inclusion criteria:**

- CBCT scans of adult Egyptian patients, males and females.
- CBCT scans with unilateral or bilateral anterior mandibles; with minimum 2 mm length distal to the mental foramen (mental foramen & anterior mandible are clearly delineated)

*Moghddam et al, 2017.*

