### **14- Study Size:**

The aim of this study is to detect the prevalence and length of the anterior loop among a sample of Egyptian population. Based upon the results of *Shariati et al 2017*, the prevalence of the anterior loop= 24.3%. Using alpha ( $\alpha$ ) level of (5%), acceptable margin of error = 6%, the minimum estimated sample size was 192 subjects. Sample size calculation was performed using Epi Info 7.2.2.2

E) Quantitative variables

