### **15- Handling of quantitative variables in analyses:**

The number of CBCT scans of Egyptian individuals with an anterior loop of the IAN will be counted and its length will be measured to estimate the variations in the Egyptian population. The length of the anterior loop will be handled as mean and standard deviation.

F) Statistical methods:

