### **16- Statistical methods:**

Data will be analyzed using IBM SPSS advanced statistics (**Statistical Package for Social Sciences**), version 21 (**SPSS Inc., Chicago, IL**). Numerical data will be described as mean and standard deviation or median and range. Categorical data will be described as numbers and percentages. A p-value less than or equal to 0.05 will be considered statistically significant. All tests will be two tailed.

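### The study is sized as 192 subjects but sampled as 192 mandible quadrants, with no rule for patients who supply two, so the 6% margin is not assured as written.

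*Combined protocol and SAP*

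**What the plan says.** Section 14 (Study Size) takes a prevalence of 24.3% from a cited study, an alpha of 5% and a margin of error of 6%, and concludes that "the minimum estimated sample size was 192 subjects". It does not say whether 24.3% is per side or per patient.

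Participants (B) ties its number to that calculation but changes the unit: "a sample of 192 CBCT images of mandible quadrants belonging to Egyptian individuals will be examined". Its next sentence speaks of scans: "The selection of the scans to be included will be based on the following eligibility criteria".

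The PO question gives the population as "mandible quadrants in Adult Egyptian Population". Section 9 admits "CBCT scans with unilateral or bilateral anterior mandibles", so one patient can supply one quadrant or two.

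Section 15 describes the count differently again: "The number of CBCT scans of Egyptian individuals with an anterior loop of the IAN will be counted". The Research question asks "How frequent is the anterior loop" without naming a unit. For the analysis, section 16 says "Categorical data will be described as numbers and percentages" and plans no confidence interval.

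No section limits a patient to one quadrant, says how two quadrants from one patient are counted, or adjusts for pairing.

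**The concern.** The same number carries two units. A calculation for independent subjects transfers to quadrants only if each quadrant comes from a different patient, or if the two sides of a patient are unrelated. Taken literally, 192 quadrants could come from as few as 96 patients (96 × 2 = 192). If left and right tend to agree, the second side adds less information than a new patient would.

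Prevalence is the primary outcome, and 6% is the only precision target in the plan. Without a rule, a reader of the results could not tell whether that target was met. Nor could the reader be certain whether the percentage is per side, per scan or per person, and these are different quantities. A person with a loop on one side only is one of two quadrants but one of one persons.

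**Working it through.** **Inputs from section 14:** p = 0.243, margin d = 0.06, alpha 5% two-sided (z = 1.96), stated n = 192.

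**Inputs not in the documents:** the share s of quadrants that belong to a pair, and the within-patient correlation rho of loop presence. Both are assumed and shown as ranges.

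**Step 1: the plan's figure.** n = z²p(1−p)/d² = 1.96² × 0.243 × 0.757 / 0.06² = 196.3. The stated 192 is within 3% of this, so I treat it as reproduced. For 192 independent units the margin is 1.96 × √(0.243 × 0.757 / 192) = 6.07 points.

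**Step 2: 192 as a cap on quadrants, 24.3% per side.** The design effect is 1 + (Σm²/Σm − 1) × rho, where m is the number of quadrants per patient. With share s paired, Σm²/Σm = 2s + (1 − s) = 1 + s, so the margin is 6.07 × √(1 + s × rho).

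| Quadrants paired | Patients | rho 0 | 0.1 | 0.3 | 0.5 | 0.7 | 1 |
|---|---|---|---|---|---|---|---|
| none | 192 | 6.07 | 6.07 | 6.07 | 6.07 | 6.07 | 6.07 |
| half | 144 | 6.07 | 6.22 | 6.51 | 6.78 | 7.05 | 7.43 |
| all | 96 | 6.07 | 6.36 | 6.92 | 7.43 | 7.91 | 8.58 |

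**Step 3: 192 as patients, every visible side read, 24.3% per side.**
- All bilateral: 384 quadrants, margin 1.96 × √(0.243 × 0.757 × (1 + rho) / 384), which is 4.3 points at rho 0 and 6.07 at rho 1.
- Half the patients bilateral: 288 quadrants, Σm²/Σm = (96 × 4 + 96) / 288 = 1.667. The margin is 4.95 points at rho 0 and 4.95 × √1.667 = 6.4 at rho 1.

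**Step 4: 24.3% as the share of patients with a loop on either side, both sides visible.** The per-side prevalence p then solves 2p − p² − rho × p(1−p) = 0.243. At rho 0.3 this gives p = 0.153. For 192 quadrants all paired, the margin is 1.96 × √(0.153 × 0.847 × 1.3 / 192) = 5.8 points. Across rho 0, 0.1, 0.3, 0.5, 0.7 and 1 it is 4.8, 5.1, 5.8, 6.5, 7.3 and 8.6 points. With half the quadrants paired it is 4.8, 5.0, 5.5, 6.0, 6.5 and 7.4.

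**Step 5: a count by scan, if section 15 means that.** With 24.3% per side and rho 0.3, a bilateral scan shows a loop on at least one side with probability 2 × 0.243 − 0.243² − 0.3 × 0.243 × 0.757 = 37.2%, against 24.3% for a unilateral scan. With half the quadrants paired (48 bilateral and 96 unilateral scans) the percentage per scan is (48 × 37.2 + 96 × 24.3) / 144 = 28.6%. A per-scan figure therefore moves with the mix of scans; a per-quadrant figure does not.

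**The case against.** The strongest reply is that the loss may be nil. If 192 means patients, which the word subjects in section 14 and the scan wording in Participants (B) and section 15 can support, bilateral scans add quadrants beyond 192 and precision is generally kept or improved (step 3). If 24.3% is a per-patient figure, the 6% target survives full pairing up to a correlation of about 0.3 and half pairing up to about 0.5 (step 4). The 8.6-point figure needs every patient bilateral and perfect left-right agreement. The study is descriptive and retrospective. All of this stands and limits the size of the point. It does not remove it, because the plan does not say which reading applies.

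A reader might infer more than the documents support:
- **That 192 is an arithmetic error.** The standard formula reproduces it within 3%.
- **That the primary outcome has no denominator at all.** The PO question names quadrants as the population and Participants (B) repeats it, so per quadrant is the most natural reading. Section 15 leaves it loose, perhaps only by wording.
- **That the planned interval would be too narrow.** Section 16 plans no interval, so undercoverage cannot be charged to the plan. It would arise only if an unclustered interval were later computed on paired quadrants.

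**Conclusion.** The point holds in a limited form. Sections 14 and B contradict each other on the unit, section 9 allows two quadrants from one patient, and nothing governs that case. The stated margin is not assured; the documents do not show that it is missed.

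The size depends on the reading. A cap of 192 quadrants with 24.3% per side gives 6.07 points without pairing and up to 8.6 at the extreme. Sampling 192 patients gives about 4.3 to 6.4. A loss of 0 to 2.5 points (8.58 − 6.07) is thus not the full range of possibilities; it applies only under the first reading. The paired share and the correlation are assumed throughout.

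One might also infer that pairing distorts the prevalence. It does not bias a per-side percentage; it only widens its uncertainty. The harm is an unclear unit and possibly overstated precision, not a reversed conclusion. It should be fixed. Confidence is high on the unit mismatch and lower on the size of any loss.

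**What to change.** Use one unit in the PO question, Participants (B), section 14 and section 15; the quadrant is the most natural choice, with section 15 then counting quadrants with a loop. State in section 14 whether 24.3% is per side or per patient. Then choose one of these:

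- **(a) One side per patient.** State in Participants (B) that the 192 quadrants come from 192 different patients, with one side chosen at random when both are eligible. The margin is about 6.07 points if 24.3% is per side. Cost: up to 96 more patients' scans to retrieve than under full pairing (192 − 96), from an archive of unstated size, and fewer measurements of loop length, a secondary outcome, because second sides go unread.
- **(b) 192 patients, every visible side.** Analyse per quadrant with clustering by patient. This roughly keeps the margin and the length data. Cost: more reading, up to 384 quadrants, each read by both radiologists and once more by one of them.
- **(c) 192 quadrants with pairs allowed.** Restate the margin in section 14 under named values for the paired share and the correlation. Cost: a less favourable margin that rests on assumptions.

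In section 16, add that prevalence is reported with a 95% confidence interval, clustered by patient whenever any patient contributes two quadrants.

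The scans are archived, so none of this needs recruitment. The choice should be made before reading begins, so that the denominator is not picked after the results are seen.

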### **9- Eligibility criteria and selection method:**

#### **✓ Inclusion criteria:**

- CBCT scans of adult Egyptian patients, males and females.
- CBCT scans with unilateral or bilateral anterior mandibles; with minimum 2 mm length distal to the mental foramen (mental foramen & anterior mandible are clearly delineated)

*Moghddam et al, 2017.*

#### **✓ Exclusion criteria**

- CBCT images of poor quality or artifacts interfering with the assessment of the anterior loop of IAN.
- Scans showing any pathosis in the interforaminal area (tumor or impaction).

### **10- Matching criteria and allocation ratio:**

Not applicable in the study

C) Variables:

[figure not shown]
**11- Details about variable**

1. Length of anterior loop's mesial extension if present.
2. Sex of the patient will be identified and addressed as the prevalence of the anterior loop of the IAN and its length may show sex predilection.

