**12- Data Sources / Measurements:**

[figure not shown]
- Retrospective Data Analysis will be performed after the CBCT images are pooled from the computer database.
- Exposure parameters of the scans were as following; scanned using Cranex® 3DX SOREDEX, 0.2 voxel resolution, 8 × 6 cm FOV, 90 kVp, 10 mA and 6 seconds exposure time
- CBCT images will be analysed using OnDemand3D ® App (Cybermed, Seoul, Korea); using the 3D module, reference lines are modified to confine with the buccolingual orientation of the inferior alveolar loop, to obtain a modified axial cut showing the inferior alveolar loop and mental foramen opening on the same plane.

In scans with an anterior loop, on the corrected axial cut the distance between the most mesial point of the mental foramen and the maximum mesial extension of the anterior loop will be measured *Von Arx et al 2013* (Figure 3).

**Figure 3:** the distance between the most mesial point of the mental foramen and the maximum mesial extension of the anterior loop will be measured *Von Arx et al 2013*

- Using the DVR module; an arch line will be drawn on the axial plane to obtain a reformatted panorama; then the mesial extension of the AL will be detected and its length will be measured by counting the number of the consecutive adjacent vertical cuts on cross-sectional view between the slice showing the anterior border of the mental foramen and the anterior border of the loop using slice interval of 1mm *Apostolakis et al 2012* (Figure 4).

**Figure 4:** Cross-sectional reconstructions showing the AL *Apostolakis et al 2012*

- CBCT images will be interpreted by two oral radiologists independently; blinded from demographic data of the patients and from the results of each other.
- Each radiologist will evaluate the images for detection of the anterior loop and measuring its length. Then one of them will re-evaluate the images with two weeks interval between the two reading sessions.
- Intra-observer and inter-observer and variability between the observers will be evaluated.

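### Age is named as an influence on the loop and is needed to apply the adult criterion, yet the written plan never records or uses it, so the sex comparison cannot be checked for age imbalance (minor)

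*Combined protocol and SAP*

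**What the plan says.** Section 6b explains why published prevalence and length vary so much. After citing differences in method, it continues "In addition to the effect of different races, age and gender". Age is thus named as a source of variation, without direction or size.

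The Specific Objectives commit the study to detect prevalence and "measure its length in relation to gender effect". Section 11 takes this up: "Sex of the patient will be identified and addressed as the prevalence of the anterior loop of the IAN", and the sentence goes on to say that prevalence and length might differ between the sexes. The only other item in that list is "Length of anterior loop's mesial extension if present". Age is not there.

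Section 9 admits "CBCT scans of adult Egyptian patients, males and females", with no age cut-off. Section 8 draws the scans from the clinical database of one private imaging centre. Section 12 has the readers "blinded from demographic data of the patients and from the results of each other". Section 10 answers the matching item with "Not applicable in the study". Section 13 asserts that bias is absent and refers only to independent blinded reading. Section 16 gives summary statistics, a two-sided 0.05 threshold and the software. It names no test, model or covariate.

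**The concern.** Section 6b names three influences. Race is narrowed by enrolling Egyptians only, and sex is the comparison of interest. Age is the one left without any handling.

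The scans come from patients already referred for dental diagnosis or treatment planning. The age mix of the men and of the women is whatever referral produced. If the ages differ and the loop varies with age among adults, part of any observed sex difference would be an age difference. Blinded reading does nothing about that. Without an age column, nobody could look for the imbalance afterwards, let alone correct it.

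Separately, a prevalence estimate for adults with no age summary leaves readers unable to judge which adults it represents.

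**Working it through.** **1. The plan's own figure.** Section 14 gives p = 0.243, margin d = 0.06, alpha = 5% and a minimum of 192.

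- n = 1.96² × 0.243 × 0.757 / 0.06² = 196.3, so 197 after rounding up. This is 5 above the stated 192, close enough to count as reproduced.
- Margin at n = 192: 1.96 × √(0.243 × 0.757 / 192) = 6.07 points.

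The 192 rests on the precision of one overall prevalence. Recording age does not change it.

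**2. Precision of the sex comparison.** The documents give no sex split. Assume 96 quadrants per sex, all independent. This is optimistic, because one person can contribute two quadrants.

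- SE of the difference = √(2 × 0.243 × 0.757 / 96) = 0.0619.
- 95% half-width = 1.96 × 0.0619 = 12.1 points.

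**3. Possible bias from age.** Treat age as two groups, and let

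- g = difference in loop prevalence between older and younger adults,
- s = difference between the sexes in the share of older patients.

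With no true sex effect, the spurious sex difference is g × s. The documents give neither input, so both are assumptions. The last column is the chance that a two-sided 5% test is significant with no true sex effect (normal approximation, SE from step 2).

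| g (assumed) | s (assumed) | Spurious difference | False-positive rate |
|---|---|---|---|
| any | 0 | 0 points | 5% |
| 10 points | 20 points | 0.10 × 0.20 = 2 points | about 6.2% |
| 20 points | 20 points | 0.20 × 0.20 = 4 points | about 9.9% |
| 20 points | 30 points | 0.20 × 0.30 = 6 points | about 16.3% |

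Against the 12.1-point half-width, 2 points is about one-sixth (2 / 12.1 = 0.17) and 6 points about one-half (6 / 12.1 = 0.50).

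**4. Data available for an adjusted model.** Expected loops = 0.243 × 192 = 46.7, about 47. A logistic model for presence can carry sex and age. The length model uses only those 47 or so loops, possibly from fewer patients.

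**5. Is age obtainable?** The adult criterion cannot be applied without age or date of birth, and Section 12 refers to patients' demographic data, though without naming items. That age is in the record is an inference, but a sound one.

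**The case against.** The strongest reply is that the sex comparison is descriptive. The research question asks how frequent the loop is and how far it extends, and the sample is sized for one prevalence. No passage claims a sex effect that is independent of age. Crude sex-specific prevalences are a valid answer to a descriptive question. This stands, and it is why the crude comparison should stay and the adjusted one be secondary.

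Section 11 is also not a complete data list: it omits presence of the loop, which is the primary outcome. A figure under the Variables heading is not available to read. Absence from the list is therefore not proof that age will go unrecorded. But no written section, including those on handling of quantitative variables and statistical methods, provides for it.

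The support for an age effect is one clause explaining variation between published studies. It says nothing specific about adults on CBCT.

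Four stronger readings are tempting and are not supported:

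- **That the sex comparison is confounded.** This needs an age effect among adults and an age difference between the sexes in this database. The documents establish neither.
- **That the plan commits to an unadjusted analysis.** Section 16 specifies no method for the sex comparison at all. Missing age adjustment is one part of that wider gap.
- **That the bias could consume the 6-point margin.** That margin belongs to overall prevalence. The relevant yardstick is the half-width of the sex difference.
- **That a formal comparison with other populations is undermined.** The plan motivates an Egyptian estimate and schedules no such comparison.

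**Conclusion.** The point holds as a minor one. The plan names age as an influence and must consult it for eligibility, yet no written section records, summarises or uses it. The sex comparison therefore cannot be checked or corrected for age, and the sample's age cannot be described. Overall prevalence, the primary outcome, is not confounded by the omission.

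Under the assumed inputs the spurious sex difference is 2 to 6 points, and zero if men and women have the same age mix. That is modest beside a half-width of about 12.1 points, which itself assumes 96 independent quadrants per sex. The case for acting is that the remedy costs little and cannot be applied later if age is not captured.

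**What to change.** - **Section 11:** add age at scan, taken from the record used to confirm adult status and kept from the readers so that the blinding in Section 12 is unchanged.
- **Reporting:** summarise age overall and by sex.
- **Section 16:** keep the crude sex comparison and show beside it, as a secondary analysis, an age-adjusted estimate: a logistic model for presence of the loop and a linear model for its length, each with sex and age.

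The cost is one data column and a slightly more complex secondary model. The length model would rest on only about 47 expected loops, so its adjusted estimate should be read with caution. Sample size, imaging and the primary estimate do not change. How to allow for two quadrants from one patient is a separate matter, and this change does not settle it.
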